2.6. Definition of Subgroups

Descriptive statistics will be performed for the primary endpoint of HDRS₁₇ change from baseline stratified by the following sub-groups.

- Screening hsCRP stratification (<3.00 mg/L, \geq 3.00 to <5.00 mg/L, \geq 5.00 to <8.00 mg/L and \geq 8.00 mg/L)
- Treatment Resistant Depression (TRD) vs. non-TRD subjects. (TRD is defined as having be treated with ≥ 2 trials of antidepressants of adequate dose and duration during the current episode.)

Other subgroups such as 5 types of maltreatment (physical abuse, physical neglect, sexual abuse, emotional abuse and emotional neglect) based on CTQ and baseline BMI status (\leq 25 (normal) vs. >25 (abnormal) or \leq 30 (normal) vs. >30 (abnormal)) may also be explored.

2.7. Incomplete/Missing Dates for Adverse Events

Treatment-emergent adverse events (AEs) for DB phase are those events with an onset date on or after the start of double-blind study medication, and occurred on or before the end of the double-blind phase. A conservative approach will be used to handle the missing dates for adverse events.

The rules for estimating incomplete AE onset dates will be as follows:

(1) The missing day of the month will be estimated as follows: If the month and year are known and double-blind study medication started during that month then the estimated date is the start date of double-blind study medication. If the month and year are known and double-blind study medication started prior to that month then the estimated date is the 1st day of the month. If the month and year are known and double-blind study medication started are known and double-blind study medication are known and double-blind study medication started prior to that month then the estimated date is the 1st day of the month. If the month and year are known and double-blind study medication started after the month, then no estimation will be done, and the AE will not be considered as treatment emergent for the double-blind phase.

(2) If both the day and the month are missing: No estimation will be performed. However, these AEs will be considered treatment emergent for the double-blind phase and will be included in the double-blind treatment summaries, except for the calculation of duration of the AE. Attempts will be made to get at least the month for the adverse events.

For incomplete AE resolution dates, the rules are:

- (1) The missing day of the month will be estimated as follows: If the month and year are known and the study medication was stopped before, or during that month, the estimated date is the last day of the month or the end of the doubleblind phase, whichever is earlier. If the study medication stopped after that month then the estimated date is the last day of the month.
- (2) If both the day and the month are missing: the estimated resolution date is the end of the double-blind phase.

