7. SAFETY

7.1. Adverse Events

Adverse events (AEs) are coded using the MedDRA dictionary (version 17.0 or above). Treatment-emergent adverse events (TEAEs) that occurred in the double-blind phase will be summarized by system organ class, preferred term, and treatment group. Adverse events that occurred in the follow up phase will be summarized separately.

Adverse events in different phases of the study are defined as below:

- Treatment-emergent adverse events during the double-blind phase are defined as AEs with an onset during the double-blind phase. In other words, treatment-emergent AE during the double-blind phase should satisfy the condition: Double-blind start date/time ≤ AE onset date/time ≤ double-blind end date. If onset time is missing and AE onset date/time is the same as the double-blind start date/time, the AE is defined to be treatment emergent in the double-blind phase.
- Adverse events during the follow up phase are defined as AEs with an onset during the follow up phase. AEs during the follow up phase should satisfy the condition: (follow up phase start date \leq AE onset date/time and AE onset date \leq follow up phase end date).

A TEAE is an event that is new in onset or increased in severity following treatment initiation. An event that starts prior to, and ends after the initiation of study medication will be considered treatment-emergent only if the severity increases after the start of medication. Adverse events will not be considered treatment-emergent if they occur or increase in severity during the follow up phase. Adverse events occurring during the follow up phase will be summarized separately. In addition, AEs will be summarized by severity and relationship to study drug using the preferred term. For the summaries of AEs by severity/relationship to study drug, the observation with the most severe occurrence/closest relationship to study drug will be chosen if there is more than one incident of an adverse event reported during the analysis phase by the subject.

Serious AEs (SAEs) and AEs that lead to study discontinuation will be summarized separately by treatment group, system organ class, and preferred term. Data listings will also be generated for deaths, other SAEs, and discontinuations due to AEs.

Adverse Events of Special Interest

Clinically relevant TEAEs of special interest will be examined in malignancies, active TB, hepatobiliary abnormalities (as defined in the protocol), and gastrointestinal perforations.

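### The onset-date rules in SAP 2.7 count a few adverse events as double-blind TEAEs although the known year or resolution date places them outside that phase

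*SAP*

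**What the plan says.** SAP section 2.7 defines double-blind TEAEs as "those events with an onset date on or after the start of double-blind study medication, and occurred on or before the end of the double-blind" period. It then announces its principle: "A conservative approach will be used to handle the missing dates for adverse events".

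Onset rule (1) covers a missing day with month and year known:

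- First dose in the same month: "double-blind study medication started during that month then the estimated date is the start date of double-blind study medication".
- First dose in an earlier month: onset becomes the first of the recorded month.
- First dose in a later month: "then no estimation will be done, and the AE will not be considered as treatment emergent for the double-blind phase".

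Onset rule (2) covers the rest: "If both the day and the month are missing: No estimation will be performed". The consequence is that "these AEs will be considered treatment emergent for the double-blind phase and will be included in the double-blind treatment summaries", apart from the duration calculation. The SAP adds that sites will be asked for at least the month.

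Section 7.1 requires the onset of a double-blind TEAE to lie between the start and end of that phase. An event already present at the first dose and continuing past it counts only if it becomes more severe after dosing starts. For the later phase: "Adverse events will not be considered treatment-emergent if they occur or increase in severity during the follow up phase".

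**The concern.** Rule (2) is triggered by the missing day and month alone. If the year is recorded, it may be enough to show that the onset was before the first dose or after the double-blind phase, yet the rule still assigns the event to that phase. Rule (1) does not behave this way: it excludes an event whose known month precedes dosing. The two rules therefore treat equally certain information differently.

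Neither onset rule looks at the resolution date. In the first-dose month this lets rule (1) impute an onset later than a known resolution and count as treatment-emergent an event that was over before the subject was dosed.

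At stake is the content of the double-blind TEAE summaries: a few events that the plan's own definitions exclude would appear in them. A programmer who notices the clash between 2.7 and 7.1 would have to settle it without guidance.

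**Working it through.** There is no stated figure to reproduce. The check applies the 2.7 onset rules literally to test dates and compares the result with what the known date parts allow. The dates are illustrative. The double-blind phase is taken to end on first dose + 83 days (12 weeks, counting the first-dose day as Day 1).

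| Case | Recorded onset | Resolution | First dose | End of DB | Result under 2.7 | What the known dates show |
|---|---|---|---|---|---|---|
| A | 2015 only | unknown | 15 Jan 2016 | 7 Apr 2016 | TEAE, rule (2) | onset before first dose |
| B | 2016 only | 10 Mar 2016 | 20 Mar 2016 | 11 Jun 2016 | TEAE, rule (2) | over before first dose |
| C | Mar 2016 | 10 Mar 2016 | 20 Mar 2016 | 11 Jun 2016 | onset set to 20 Mar 2016, TEAE, rule (1) | over before first dose |
| D | 2017 only | unknown | 20 Sep 2016 | 12 Dec 2016 | TEAE, rule (2) | onset after end of DB |
| E | Feb 2016 | unknown | 20 Mar 2016 | 11 Jun 2016 | not a TEAE | onset before first dose |
| F | Aug 2016 | unknown | 20 Mar 2016 | 11 Jun 2016 | onset set to 1 Aug 2016, not a TEAE | onset after end of DB |
| G | 2016 only | unknown | 20 Mar 2016 | 11 Jun 2016 | TEAE, rule (2) | ambiguous |

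**Reading the table.**

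- A to D are counted as double-blind TEAEs although the known information places the onset outside that phase. In A, section 7.1 would admit the event only if it worsened after dosing; rule (2) admits it without that test. D is the case that 7.1 excludes outright.
- In C the imputed onset (20 March) is 20 − 10 = 10 days after the recorded resolution (10 March).
- E and F are controls: with the month known, rule (1) already gives the right answer.
- G is truly ambiguous. Counting it is what a conservative rule is for, and it stays a TEAE under the fix below.

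**How often the year alone can decide.** Section 1.2 gives screening of up to 4 weeks (28 days) and a follow-up of 14 weeks (98 days). Assume that first doses are spread evenly over the year, that these phases run their full length, and that events are recorded from the start of screening. A new year then falls

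- between the start of screening and the first dose for 28/365 = 7.7% of subjects;
- within follow-up for 98/365 = 26.8%, about 27%, of subjects.

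These are shares of subjects in whom the year-based error is possible, not error rates. Such a subject must also have an event with only the year recorded. Case C needs no new year, but it does need an onset recorded to the month, in the first-dose month, with a complete resolution date before dosing. The SAP gives no count for either pattern.

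**The case against.** The strongest reply is that 2.7 is a deliberate over-counting convention, that it is the specific rule for dates that cannot be placed, and that 7.1 supplies the general definition. On that reading there is no conflict, only a sentence missing on which one yields. This holds for ambiguous dates such as case G. It does not hold for A to D, where the dates are incomplete but can still be placed.

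Several limits do stand:

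- A reader might infer that the onset rules as a whole ignore a known year. They do not: rule (1) uses month and year, and only rule (2) disregards the year. A resolution date, for its part, can only show that an event was over before treatment; it cannot show a follow-up onset.
- A reader might infer that every event with an incomplete onset is misclassified. Most are either handled correctly or truly ambiguous.
- A reader might infer that the comparison between arms is diluted. The document does not support that: section 7.1 plans descriptive summaries by treatment group, with no test of event rates, and the rules are the same in both arms.
- A reader might infer that negative durations are widespread. Events under rule (2) are left out of the duration calculation, so only the first-dose-month case under rule (1) can produce one, and 7.1 plans no duration summary.
- Asking sites for the month will reduce the number of year-only onsets.

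A correction that simply excluded every onset known to precede dosing would also do harm, because it would drop events that worsen on treatment, which 7.1 counts.

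**Conclusion.** The point holds in a narrow form. Rule (2) lacks a condition on the year, and rule (1) lacks a check against a complete resolution date in the first-dose month. Followed literally, each gives a result that the definitions in 2.7 and 7.1 exclude. This is a stated rule with a wrong outcome in identifiable cases, not a missing detail.

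The effect is probably small and cannot be put as a number of events, since the SAP gives no count of partial dates. The 7.7% and 27% bound only the subjects in whom the year could decide, and they rest on evenly spread first doses, full-length phases and recording from the start of screening. No bias in the treatment comparison has been shown. It is a minor point, worth correcting because the correction is simple and leaves the conservative intent intact.

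**What to change.** Insert in section 2.7, ahead of onset rules (1) and (2), statements to this effect:

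1. An event whose complete resolution date precedes the first dose is not a double-blind TEAE.
2. An event whose known onset month or year ends before the first dose is treated as a pre-treatment onset. It is a TEAE only if it worsens after the first dose during the double-blind phase, as 7.1 states.
3. An event whose known onset month or year begins after the end of the double-blind phase is a follow-up event.
4. Rules (1) and (2) apply only to onset dates that remain ambiguous after steps 1 to 3.

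No separate cap of the imputed onset at the resolution date is needed when that date is complete. After step 1 the imputed onset is either the first dose, which is no later than the resolution, or the first of the recorded onset month.

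The cost is a few lines of SAP wording and a short derivation check, for which cases A to G can serve as test records. No new data are needed.

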1.1. Trial Objectives

Primary Objective

To evaluate the efficacy of sirukumab as adjunctive treatment to antidepressant therapy (monoaminergic antidepressant) where sirukumab (administered as a 50mg subcutaneous (SC) injection at Day 1, Day 28 and Day 56 during the 12-week double-blind treatment period) is compared to adjunctive placebo based on the change from baseline to 12-week endpoint in depressive symptoms as measured by the total score on the Hamilton Depression Rating Scale (HDRS₁₇), in subjects diagnosed with Major Depressive Disorder (MDD) who have had a suboptimal response to the current standard oral antidepressant therapy and have a screening high sensitivity C-Reactive Protein (hsCRP) \geq 0.300 mg/dL (International System of Units (SI) 3.00 mg/L).

Secondary Objectives

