1.2. Trial Design

This is a multicenter, double-blind, placebo-controlled study in male and female subjects, 21 to 64 years of age inclusive, with major depressive disorder (MDD) who have had a suboptimal response to standard oral antidepressant therapy; have failed no more than 3 antidepressant treatments in the current major depressive episode.

The study will consist of 3 phases: a screening phase of up to 4 weeks, a 12-week doubleblind treatment phase, and a 14-week posttreatment follow-up phase. The total duration of subject participation will be approximately 26 weeks.

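### The imputation rules for partial AE resolution dates cap at the end of the double-blind phase, which overrides a recorded later month and, if applied to follow-up events, puts resolution before onset

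*SAP*

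**What the plan says.** SAP section 2.7 gives two rules for incomplete resolution dates.

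- **Rule (1), day missing.** The first branch applies thus: "If the month and year are known and the study medication was stopped before, or during that month". Its result is: "the estimated date is the last day of the month or the end of the doubleblind phase, whichever is earlier". The second branch reads: "If the study medication stopped after that month then the estimated date is the last day of the month".
- **Rule (2), day and month missing.** Here "the estimated resolution date is the end of the double-blind phase".

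Neither rule refers to the onset date, and neither is restricted to events that began in the double-blind phase. The section introduces its rules with the statement: "A conservative approach will be used to handle the missing dates for adverse events". It implies that durations are derived, because onset rule (2) includes certain events in the summaries "except for the calculation of duration of the AE".

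Other sections give the setting. Section 1.2 provides for "a 14-week posttreatment follow-up phase". Section 2.3.1 starts that phase on the day after the double-blind phase ends. Section 2.5.5 defines a safety set for follow-up, and section 7.1 summarises follow-up adverse events separately.

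**The concern.** Imputing a missing day should place the event somewhere inside the month that was recorded. The cap in rule (1) can move the date out of that month, to a point at which the site's record says the event was still ongoing. For an event that starts in follow-up, the cap precedes onset, so the derived duration is zero or negative. Rule (2) has the same effect on such events. The durations affected are those of events that outlast the double-blind phase.

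**Working it through.** The plan gives no figure to reproduce on this point. The check applies the rule as written.

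**Inputs**
- Last planned dose on Day 56 (section 1.1: "administered as a 50mg subcutaneous (SC) injection at Day 1, Day 28 and Day 56").
- End of the double-blind phase taken as Day 84 (12 weeks; the Week 12 target day in Table 1).
- End of follow-up: 84 + 14 × 7 = Day 182.
- Assumptions: illustrative calendar dates, and duration = resolution − onset + 1, because section 2.7 gives no duration formula.

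**Rule (1) as a formula.** Let M be the last day of the recorded month and E the end of the double-blind phase. If medication stopped on or before M, the imputed date is min(M, E); otherwise it is M. Medication stops no later than E, so every month that ends after E falls in the capped branch and the imputed date is E.

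**Case A: double-blind onset, recorded month wholly after E.** The first day of the month is later than E, so the imputed date always precedes the recorded month.
- First dose 5 January 2015 gives last dose 1 March and E = 29 March.
- Onset 20 March, resolution recorded as May 2015: imputed date 29 March.
- Duration under the rule: 29 − 20 + 1 = 10 days.
- Shortest duration consistent with the record (1 May): 12 + 30 + 1 = 43 days.
- Duration to month end (31 May): 12 + 30 + 31 = 73 days.

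**Case B: follow-up onset, fully known.** M ≥ onset ≥ E + 1, so min(M, E) = E, which is at least one day before onset.
- Same subject, onset 20 April, resolution recorded as May 2015: imputed date 29 March.
- Duration under the rule: −22 + 1 = −21 days.
- Duration to month end: 11 + 31 = 42 days.
- Rule (2) also returns E, so the reversal is the same.

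**Case C: recorded month ends on or before E.** The cap does nothing.
- First dose 20 January 2015 gives last dose 16 March and E = 13 April.
- Resolution recorded as March 2015: min(31 March, 13 April) = 31 March, although medication had already stopped.

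**Range.** The rule was run over every first-dose date in one year, with events out to Day 182.

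| Situation | Faulty dates | Displacement |
|---|---|---|
| A: imputed date before the first day of the recorded month | 850,528 of 850,528 | 1 to 98 days |
| B: imputed date before a known onset | 602,250 of 602,250 | 1 to 98 days |
| Onset and true resolution both in the double-blind phase: imputed date before onset | 0 of 444,570 | none |

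The maximum is 182 − 84 = 98 days. If follow-up is taken to end at the last visit in Table 1 (Week 22, Day 154), it is 154 − 84 = 70 days. The counts confirm the logic; they do not estimate how often this would happen in the trial.

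**Limit on case B.** If the onset day is also missing and the onset month is the one in which the double-blind phase ended, the onset rule sets onset to the first of that month or to the first-dose date. The reversal may then not appear.

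**The case against.** The strongest defence concerns scope. Section 2.7 opens with treatment-emergent events of the double-blind phase, and its onset rules are keyed to the start of double-blind medication. Section 7.1 handles follow-up events separately. The cap may therefore be meant only to count duration up to the end of the double-blind phase, in which case negative durations for follow-up events do not arise. This reading is plausible, so the reversal in case B is conditional on scope. However, the section does not state the limit, and no other rule covers partial dates of follow-up events. Case A stands on either reading, because a recorded later month is still replaced for an event with double-blind onset.

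A reader might infer three stronger points that the document does not support:
- **That every partial resolution date after medication stops is cut back.** It is not; case C shows a month end that is kept.
- **That the safety tables are biased.** Section 7.1 specifies summaries of incidence, severity, relationship, serious events and discontinuations, and no duration table. Treatment emergence depends on onset and worsening severity. The one use of an end date there, for events that began before treatment and end after its start, is not altered by a cap at the end of the double-blind phase.
- **That the cap breaks the promise of a conservative approach.** That sentence follows the definition of treatment emergence and may concern attribution only. The plan does not say that conservative means longer duration.

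**Conclusion.** The point holds in a limited form. As written, rule (1) gives a date that contradicts the record whenever the recorded resolution month lies wholly after the double-blind phase. If section 2.7 applies to follow-up-onset events, both rules also put resolution before a known onset. Each displacement is between 1 and 98 days, given a double-blind phase that ends on Day 84 and a full 14-week follow-up. The number of events affected is unknown, because the plan gives no basis for the frequency of partial dates.

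Materiality is low. Derived durations and any listing that shows imputed dates would be wrong. Treatment-emergent status, incidence tables and efficacy results would not change. This is a desirable correction of wording, not a threat to the trial's conclusions.

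**What to change.** In section 2.7:

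- **Rule (1):** impute the earlier of the last day of the recorded month and the overall reference end date defined in section 2.3.2.
- **Rule (2):** impute the earlier of 31 December of the recorded year, if known, and the overall reference end date. Without the 31 December bound, the date could fall after the recorded year.
- **Both rules:** require the imputed resolution date to be no earlier than onset.
- **If duration truncated at the end of the double-blind phase is wanted:** define it as a separate double-blind-phase duration, for events with double-blind onset only, and leave the imputed resolution date uncapped.

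The cost is a few phrases in the SAP and the matching derivation code; no other analysis changes. There is one small downside: the new rule (2) may lengthen the duration of some double-blind-phase events with day and month missing, because it may place their resolution as late as the end of follow-up.

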3. SUBJECT INFORMATION

3.1. Demographics and Baseline Characteristics

Demographic and baseline characteristics (Table 2) and psychiatric history at baseline (Table 3) will be summarized by treatment group for the All Randomized analysis set. The continuous variables will be summarized using descriptive statistics (N, mean, standard deviation [SD], median, minimum, and maximum). The categorical variables will be summarized using a frequency distribution with the number and percentage of subjects in each category.

Table 2:Demographic Variables and Baseline Characteristics		
Continuous Variables:		
• Age (years) (informed consent date – date of birth + 1) / 365.25		
• Baseline weight (kg)		
• Baseline height (cm)		
• Baseline BMI (kg/m2) calculated as Weight (kg)/[Height (m)] ²		
Baseline hsCRP level		
Categorical Variables:		
• Sex (male, female)		
• Race ^a (White, Black or African American, Asian, American Indian or Alaskan native,		
Native Hawaiian or Pacific islander, other)		
• Ethnicity (Hispanic or Latino, not Hispanic or Latino)		
• Baseline hsCRP (< 3.00 mg/L, ≥3.00 to <5.00 mg/L, ≥5.00 to <8.00 mg/L and ≥8.00 mg/L)		

a If multiple race categories are indicated, then Race is recorded as "Multiple".

Table 3: Psychiatric History at Baseline Variables		
Continuous Variables:		
• Baseline HDRS ₁₇		
Baseline IDS-C30 total score		
Baseline CGI-S score		
Categorical Variables:		
Baseline CGI-S score		
• Antidepressant treatment history (as obtained in the MGH-ATRQ)		

